## 1. Study Identification

- 1.1. Unique Protocol Identification Number:
- 1.2. **Brief Title:** The effects of fish oil supplementation on the brain health of collegiate football athletes.
  - 1.2.1. **Acronym:** not required
- 1.3. **Official Title:** Study of Effect of Docosahexaenoic Acid (DHA) and Eicosapentaenoic acid (EPA) Supplementation on Biomarkers of Sub-Concussion Injuries in American Football.
- 1.4. **Secondary ID:** not required
- 1.5. **Study Type:** Interventional (clinical trial)

# 2. Study Status

- 2.1. **Record Verification Date:** Month: Year:
- 2.2. Overall Recruitment Status: Completed: The study has concluded normally; participants are no longer receiving an intervention or being examined (that is, last participant's last visit has occurred)
  - 2.2.1. Why Study Stopped: NA
- 2.3. **Study Start date:** May 29, 2019
- 2.4. **Primary Completion date:** January 28, 2020
- 2.5. **Study Completion Date:** January 28, 2020

#### 4. Oversight

- 4.1. Studies a U.S. FDA-regulated Drug Product: No
- 4.2. Studies a U.S. FDA-regulated Drug Product: NA
- 4.3. **US FDA IND or IDE:** No
- 4.4. **Product Manufactured in and Exported from U.S:** Yes
- 4.5. **Human Subjects Review:** Yes
- 4.6. Human Subjects Protection Review Board Status: Submitted, approved

Study Title: Study of Effect of Docosahexaenoic Acid (DHA) and Eicosapentaenoic acid (EPA) on Biomarkers

of Sub-concussion Injuries in American Football.

IRB #: 1904553365

4.7. Data Monitoring Committee: Yes4.8. FDA Regulated Intervention: No

### 5. Study Description

5.1. **Brief Summary:** A short description of the clinical study, including a brief statement of the clinical study's hypothesis, written in language intended for the lay public. Limit: 5000 characters.

American football is one of the most popular sports in the U.S. Yet this sport is associated with increased risk of concussion (also known as mild traumatic brain injury, or mTBI) and subconcussive injury from repeated head impacts (RHI) due to the aggressive and highspeed nature of the game. Current protective equipment used by players are not sufficient to reduce concussion incidence and severity, nor are there any therapeutics available to prevent concussion. This study is a randomized, double-blind, placebo controlled trial, including 38 research participants, to determine whether an omega-3 polyunsaturated fatty acids (PUFA) fish oil supplement containing 3.0 grams of docosahexaenoic acid (DHA; 22:6n-3) and eicosapentaenoic acid (EPA; 20:5n-3) can reduce blood biomarkers of sub-concussion injuries compared to placebo (high-oleic safflower oil) over a course of the American football season among collegiate football athletes. Secondary outcomes include 1) determining the effect of daily DHA and EPA supplementation on brain imaging markers of sub-concussion injuries, and 2) a responder analysis to determine whether genotype differences in fatty acid desaturase 1 (FADS1), FADS2, elongation of very long chain fatty acids 2 (ELOVL2), and ELOVL5 genes affect treatment outcome of DHA. An exploratory outcome is the discovery of novel and more sensitive metabolic or lipidomic biomarkers of sub-concussion injury. The dosage of DHA/EPA used in this study is generally safe, and procedures involved, monthly blood draws, surveys, and Magnetic Resonance Imaging (MRI), pose minimal risks to participants. While this study provides no direct benefit to participants, successful outcomes of this study can benefit the society by shedding light on development of potential preventative therapeutics for sports-induced mTBI and brain injury from RHI. The risk-benefit profile is appropriate for conducting this study. Based on preclinical studies and previous clinical study results, we expect that in comparison to placebo treatment, DHA and EPA treatment throughout the course of one American football season can maintain lower levels of sub-concussion associated biomarkers,

Study Title: Study of Effect of Docosahexaenoic Acid (DHA) and Eicosapentaenoic acid (EPA) on Biomarkers

of Sub-concussion Injuries in American Football.

IRB #: 1904553365

inflammatory cytokines, and cardiovascular risk markers. We also expect participants treated with DHA and EPA to have lower brain MRI imaging markers of sub concussion injury.

5.2. **Detailed Description:** (not required) Definition: Extended description of the protocol, including more technical information (as compared to the Brief Summary), if desired. Do not include the entire protocol; do not duplicate information recorded in other data elements, such as Eligibility Criteria or outcome measures. Limit: 32,000 characters.

# 6. Conditions and key words

- 6.1. **Primary Condition Being Studied:** Sub-concussive brain injury as measured by biomarkers of axonal damage from repeated head impacts (RHI).
- 6.2. **Keywords:** (not-required) concussion, mTBI, repeated head impacts, football, brain, Chronic traumatic encephalopathy, Magnetic resonance imaging, Neurofilament light chain, biomarker

### 7. Study design

- 7.1. **Primary Purpose:** Prevention
- 7.2. Study Phase: NA
- 7.3. **Interventional Study Model:** Parallel
- 7.4. **Model Description:** Participants will be randomized to treatment (3 grams DHA and EPA (2:1 weight ratio)) or placebo (3 grams high-oleic safflower oil) in a 1:1 allocation ratio based on their position on the football team and roster depth (starter vs. non-starter). Participants will be recruited as a single cohort. After screening, participants will be treated with DHA and EPA or matching placebo for 25 weeks (a full course of an American football season, including summer camp training sessions). A follow-up visit is scheduled 7 weeks after the final dosing at week 32 for recovery and adverse event evaluation.
- 7.5. **Number of Arms:** Two
- 7.6. **Masking Roles:** Participant, investigator, care provider, outcomes assessor
- 7.7. **Masking Description:** Study personnel will be kept blind to treatment assignments. The treatment assignment for each participant will be available to the investigator in a sealed envelope that may be opened only in the case of a serious adverse event which the investigator feels cannot be adequately treated without knowing the identity of the study medication. Code breakers will be collected and reviewed at the end of the study. If the blinding has been broken, then the investigator will provide documentation regarding the fact and indicate the other staff that received this information.
- 7.8. **Allocation:** Randomized
- 7.9. **Enrollment Type:** Actual
- 7.10. Number of Subjects: 38

# 8. Arms, Groups, and Interventions

3

Study Title: Study of Effect of Docosahexaenoic Acid (DHA) and Eicosapentaenoic acid (EPA) on Biomarkers

of Sub-concussion Injuries in American Football.

IRB #: 1904553365

- 8.1. **Arm 1 Type:** Active comparator
- 8.2. **Arm 1 Title:** Treatment
- 8.3. **Arm 2 Type:** Placebo Comparator
- 8.4. **Arm 2 Title:** Placebo
- 8.5. **Intervention 1:** 
  - 8.5.1. **Intervention 1 Type:** Dietary Supplement
  - 8.5.2. **Intervention 1 Name:** Fish oil supplement containing docosahexaenoic acid (DHA; 22:6n-3) and eicosapentaenoic acid (EPA; 20:5n-3)
  - Intervention 1 Description: Participants consumed a dietary supplement consisting of 3 8.5.3. grams refined fish oils as DHA and EPA ethyl esters in 2:1 ratio 5 days a week for 25 weeks. The product is stabilized with identity preserved mixed natural tocopherols and maintains stability for 24 months when stored in original, unopened, light-resistant containers at a temperature below 30° Celsius. Refined fish oil was encapsulated so six capsules provide 3 gram per dose. Certificate of analysis confirming manufacture date, active ingredient, fill weight, and microbiology safety, and disintegration time was provided. A dose of 3 grams DHA and EPA, 5 days per week, was based on a previous clinical study in a similar population using the same compounds. This dose is considered generally safe, and can provide sufficient bioavailability to significantly reduce plasma NfL level (a biomarker of brain injury and neurodegeneration). The dose remained constant for each participant during the study period. If a participant experiences an adverse event (AE) considered to be possibly related to the study dietary supplement, the investigator has the option to split up the dose throughout the day, recommend the participant take the supplement with food or to discontinue the participant.
- 8.6. **Intervention 2:** 
  - 8.6.1. **Intervention 2 Type:** Placebo
  - 8.6.2. **Intervention 2 Name:**
  - 8.6.3. **Intervention 2 Description:** Participants consumed a placebo consisting of encapsulated high-oleic safflower oil. Each placebo capsule contains 866.9 mg/capsule active ingredient. The placebo intervention included consumption of 6 capsules 5 days a week for 25 weeks. A certificate of analysis confirming manufacture date (06/03/2019), active ingredient (safflower oil), fill weight (866.9 milligrams), and microbiology safety (all negative), and disintegration time (3 minutes) was provided.
- 8.7. **Arm/Intervention Cross-Reference:** Arm 1 = Intervention 1; Arm 2 = Intervention 2
- 9. Outcome Measures
  - 9.1. Outcome 1: Primary Outcome Measure
    - 9.1.1. **Title 1:** The effect of DHA and EPA Omega-3 PUFA fish oil supplementation on blood biomarkers of brain injury compared to placebo (high-oleic safflower oil) over a course of

Study Title: Study of Effect of Docosahexaenoic Acid (DHA) and Eicosapentaenoic acid (EPA) on Biomarkers of Sub-concussion Injuries in American Football.

IRB #: 1904553365

the American football season among collegiate football athletes exposed to repeated subconcussive head impacts.

- 9.1.2. **Time Frame 1:** 32 weeks from baseline to one month postseason/treatment
- 9.1.3. **Description 1:** (not required) Blood-based biomarkers for sub-concussion injury (neurofilament light (NFL), Tau protein (Tau), ubiquinone C-terminal hydrolase L1 (UCH-L1)) and can lower inflammatory cytokines (C-reactive protein (CRP), tumor necrosis factor 1 (TNF-α), interleukin 6 (IL6)) will be measured at baseline, mid-treatment, post treatment, and one month (recovery) after the end of treatment and the football season.

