### 9.2. Outcome 2: Primary Outcome Measure

- 9.2.1. **Title 2:** The effect of DHA and EPA Omega-3 PUFA fish oil supplementation on blood cholesterol, low-density lipoprotein (LDL), high-density lipoprotein (HDL), and triglyceride levels in collegiate football athletes.
- 9.2.2. **Time Frame 2:** 25 weeks from baseline to end of treatment
- 9.2.3. **Description 2:** (not required) A lipid panel will be assessed at baseline and end of treatment.

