# Power, Sample size, and Confidence intervals

This study is both an independent replication of a previous omega-3 supplementation trial with college football players, as well as an exploratory, hypothesis-generating extension that will collect additional biological data including cardiometabolic biomarkers and untargeted lipidomics. For statistical power, our primary hypothesis-driven question is whether DHA+EPA supplementation will have a protective or restorative effect based on measured levels of markers of neuronal damage, such as NFL, and whether this will vary by starter/non-starter. In this study, with a samples size of n=44 starters, n=44 non-starters, and a significance level of  $\alpha$ =0.05, we have 80% power to detect an effect size of d = 0.6, where d=( $\mu_1 - \mu_2$ )/ $\sigma$ , is the difference in the group means divided by the pooled standard deviation. The TCU study looked at the differences between starters and non-starters at multiple time points and found effect sizes ranging from 0.88 to 2.07. The TCU study also found dramatic changes in NFL levels between starters on placebo, with levels more than doubling over the season, while starters on supplementation saw a more modest increase of 35% by the end of the season. If we look only at starters, and compare the supplement (n=22) and placebo groups (n=22), we are powered to see an effect size of 0.86, well below the reported differences at many time points in the TCU study. We anticipate some other biomarkers will also change over time, and we are

well-powered to detect small to moderate effects. For previously unstudied biomarkers, our focus will be on estimating the magnitude and direction of effects in order to discover which are the most informative as markers of brain injury/recovery or omega-3 supplementation.

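### The protocol labels seven to ten blood measures primary, the SAP's primary question covers only neuronal-damage markers, and neither document gives a multiplicity rule for the primary tier

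*Protocol*

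**What the plan says.** **Protocol, section 9.** Outcome 1 is a primary outcome. Its title (9.1.1) concerns the effect of "fish oil supplementation on blood biomarkers of brain injury compared to placebo". Its description (9.1.3) begins "Blood-based biomarkers for sub-concussion injury (neurofilament light (NFL), Tau protein (Tau), ubiquinone C-terminal hydrolase L1 (UCH-L1)) and can lower inflammatory cytokines" and goes on to name CRP, TNF-alpha and IL-6, measured at baseline and three later times. Its time frame (9.1.2) is "32 weeks from baseline to one month postseason/treatment". Section 9.2 is headed "Outcome 2: Primary Outcome Measure" and concerns the effect "on blood cholesterol, low-density lipoprotein (LDL), high-density lipoprotein (HDL), and triglyceride levels in collegiate football athletes", assessed at baseline and end of treatment (9.2.3).

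**Protocol, 5.1 Brief Summary.** The main aim is whether the supplement "can reduce blood biomarkers of sub-concussion injuries compared to placebo". The clinical lipid panel is in none of the tiers listed there. The closing statement of expected results names inflammatory cytokines and cardiovascular risk markers separately from the sub-concussion biomarkers and gives them no tier.

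**SAP, Power section.** The primary question is a protective or restorative effect on "measured levels of markers of neuronal damage, such as NFL", "and whether this will vary by starter/non-starter". Cardiometabolic biomarkers belong to a hypothesis-generating extension. Alpha of 0.05 appears once, for the power calculation. Previously unstudied biomarkers are for estimation.

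**SAP, Continuous outcome measures.** The list is unranked: NfL; TNF-a and IL-6, labelled cardiometabolic; triglycerides, HDL-C and LDL-C; and 23 fatty acids. Tau, UCH-L1, CRP and total cholesterol are not named.

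**The concern.** A reader cannot tell which measures may support a positive primary claim. The protocol's labels admit seven or ten, while the SAP's primary question admits neuronal-damage markers only. TNF-alpha and IL-6 may be primary in the protocol but carry the SAP's exploratory label.

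With no order, adjustment or success rule, an isolated p<0.05 on a lipid or a cytokine could be presented as a primary success even if NfL, the marker studied in the trial being replicated, showed no effect. No single visit is fixed for Outcome 1, and the SAP adds a treatment by starter interaction, so several tests per measure are also possible.

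**Working it through.** **1. Count of primary measures.** By the titles: 3 (NfL, Tau, UCH-L1) + 4 (cholesterol, LDL, HDL, triglycerides) = 7. With the three cytokines in 9.1.3: 6 + 4 = 10. The SAP's own question, using the neuronal markers that the protocol names: 3.

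**2. The plan's power figures.** A two-sample t-test at two-sided 0.05 (sidedness is not stated, so assumed) gives 79.5% power for 44 vs 44 at d=0.6, and 79.6% for 22 vs 22 at d=0.86. Both match the SAP's 80%, but only for one test at an unadjusted 0.05.

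**3. Chance of at least one nominal success when nothing works.** Each measure is tested once at 0.05 and any success counts. For k independent tests this is 1 − 0.95^k. The correlated columns use equicorrelated normal statistics and numerical integration; the correlations are assumptions, since the documents give none.

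| Measures | Independent | Correlation 0.5 | Correlation 0.7 |
|---|---|---|---|
| 3 (neuronal markers) | 1 − 0.95^3 = 14% | 13% | 11% |
| 7 (by title) | 1 − 0.95^7 = 30% | 23% | 18% |
| 10 (with cytokines) | 1 − 0.95^10 = 40% | 29% | 21% |

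**4. Outcomes 1 and 2 as separate families, independent tests.** Outcome 1: 14% with three measures, or 1 − 0.95^6 = 26% with six. Outcome 2: 1 − 0.95^4 = 19%.

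**5. More than one test per measure.** Six Outcome 1 measures at three post-baseline visits plus four lipids at one visit make 6 × 3 + 4 = 22 tests. Even at the ten-measure threshold of 0.05/10 = 0.005, the chance is 1 − 0.995^22 = 10% if independent, before any starter interaction. Holm over ten measures therefore holds 5% only with one test per measure.

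**6. Power cost of Holm.** Protocol 7.10 gives 38 players; 19 per arm and a simple t-test without baseline adjustment are assumed. The first Holm step is the strictest threshold that NfL could face.

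| Threshold | d detectable with 80% power | Power at d=0.93 |
|---|---|---|
| 0.05 | 0.93 | 80% |
| 0.05/7 = 0.0071 | 1.21 | 52% |
| 0.05/10 = 0.005 | 1.25 | 47% |

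**The case against.** The strongest reply is that the plan already has a hierarchy. The SAP has one hypothesis-driven question, about neuronal damage; it calls many analyses exploratory and plans estimation for previously unstudied biomarkers. Outcomes 1 and 2 ask different questions over different periods (32 and 25 weeks), so they can be treated as separate families. On that view the 30% and 40% figures pool what need not be pooled.

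Much of this stands. The pooled figures need a single family and an any-success rule, and neither document states either. A reader might infer that the plan adopts such a rule, or that its false-positive rate simply is 30% to 40%. The text does not support that; it only fails to exclude it. If all primary measures had to succeed, no adjustment would be needed, but that rule is not stated either.

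The reply does not remove the problem. Three neuronal markers alone give 11% to 14%, and separate families give 14% to 26% and 19%. The SAP offers NfL as an example, so it does not make NfL the sole primary. Its statements on exploratory work do not say which of the protocol's primary measures they cover.

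A reader might also infer that the SAP dropped Tau, UCH-L1, CRP and total cholesterol. Its list is worded as open, so they may fall under the same mixed model; the SAP does not say.

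**Conclusion.** The point holds as an unresolved definition of the primary tier. Two outcomes are labelled primary, they cover seven or ten measures, the SAP's primary question is narrower, and no rule governs claims within the tier. Under no effect, the chance of at least one nominal primary success ranges from 11% (three markers, correlation 0.7) to 40% (ten independent measures), against 5% for one measure with one contrast. Several visits and the starter interaction would add to this.

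These figures assume two-sided 0.05, one test per measure, and that any one success counts; the correlations are also assumed. They are not the probability that a given positive result is false, and they do not show that anyone has made or intends such a claim. This should be corrected, and the correction is cheap.

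**What to change.** **In every case.** Make Protocol section 9 and the SAP name the same primary set and say whether the cytokines belong to it. For each primary measure give exactly one prespecified treatment contrast: a visit or an average, and the role of starter status. Before fixing the contrast, reconcile the one-month interval in 9.1.2 with Protocol 7.4, which places the week-32 visit seven weeks after final dosing. Add Tau, UCH-L1, CRP and total cholesterol to the SAP list, or state that they were not assayed. State the unblinding date: Protocol 2.2 reports the study completed, but neither document says whether codes were broken.

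**If codes are still blinded.** Name NfL as the single primary at two-sided 0.05. Treat the other measures as secondary under Holm, or as estimates with confidence intervals and no claim.

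**If data are already unblinded.** Keep all ten measures primary under Holm, with one contrast each. Date and disclose the change, including that the contrasts were chosen late. This avoids narrowing the set after results are known, though it also tests measures that the SAP calls exploratory.

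**Cost.** Wording only, provided the planned assays were run. With NfL as sole primary, the other measures lose primary status. Under Holm, NfL may need p≤0.0071 (seven measures) or p≤0.005 (ten), with the loss of power shown in the working.

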### 9.2. Outcome 2: Primary Outcome Measure

- 9.2.1. **Title 2:** The effect of DHA and EPA Omega-3 PUFA fish oil supplementation on blood cholesterol, low-density lipoprotein (LDL), high-density lipoprotein (HDL), and triglyceride levels in collegiate football athletes.
- 9.2.2. **Time Frame 2:** 25 weeks from baseline to end of treatment
- 9.2.3. **Description 2:** (not required) A lipid panel will be assessed at baseline and end of treatment.

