#### Continuous outcome measures include:

- Biomarkers NFL
- Cardiometabolic markers TNF-a, IL-6
- Lipid panel TG, HDL-C, LDL-C
- GC-FID for both RBC and Plasma results in 23 free fatty acids concentrations

For these continuous outcomes, we will use a longitudinal mixed-effects model framework to look at both individual and group-level changes from baseline over time. Outcome measures will be transformed where appropriate (e.g., log, sqrt, Box-Cox). Covariates will include age, position, genotypes, treatment, and starter/non-starter, as well as a treatment x starter/non-starter interaction. We will also graphically explore the trajectories of the different biomarkers over time.

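### The SAP's model for the two-visit lipid panel, a primary outcome, lists neither the baseline value nor a treatment-by-visit term, so the arm contrast is undefined and may be imprecise or diluted.

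*Protocol*

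**What the plan says.** Protocol 9.2 is headed "Outcome 2: Primary Outcome Measure". It covers total cholesterol, LDL, HDL and triglycerides over "25 weeks from baseline to end of treatment", and its description reads: "A lipid panel will be assessed at baseline and end of treatment". Each player therefore has at most two lipid values. The neuronal and inflammatory markers of Outcome 1 (Protocol 9.1.3), by contrast, "will be measured at baseline, mid-treatment, post treatment, and one month (recovery) after the end of treatment": four occasions.

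The SAP, under continuous outcome measures, lists "Lipid panel TG, HDL-C, LDL-C" beside NFL, TNF-a, IL-6 and the fatty acids. For all of them it says "we will use a longitudinal mixed-effects model framework to look at both individual and group-level changes from baseline over time". On model terms it says: "Covariates will include age, position, genotypes, treatment, and starter/non-starter, as well as a treatment x starter/non-starter interaction".

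The SAP does not say whether the baseline lipid value is a response, a covariate or subtracted out. It does not say whether baseline means are held equal between arms, or which random effects are used. It names no visit term and no treatment-by-visit term. Total cholesterol is in the protocol's outcome title but not in the SAP's lipid list.

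**The concern.** One generic model description has to serve outcomes with four visits and a primary outcome with two. For the two-visit outcome the missing details decide what is estimated.

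- Change from baseline as the response, with no baseline covariate, is a change-score analysis. So is a treatment-by-visit model with free baseline means. Both give up precision that the baseline sample could supply.
- Baseline among the responses, with only the listed treatment main effect, averages a difference expected to be zero (before treatment) with the difference of interest (after treatment). The estimate is then diluted as well as imprecise.

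This matters more because the protocol reports 38 participants, while the SAP's power statement is for 44 + 44. The SAP also announces interest in individual change, which two visits support only in a limited sense.

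**Working it through.** **The plan's own figures.** The SAP states 80% power for d = 0.6 with 44 vs 44, and d = 0.86 with 22 vs 22, at alpha 0.05. A two-sided two-sample t-test gives 79.5% and 79.6%. Both reproduce; neither is specific to lipids.

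**Inputs.** Two lipid visits (Protocol 9.2.3). 38 participants (Protocol 7.10), allocated "in a 1:1 allocation ratio" (Protocol 7.4), so n = 19 per arm is assumed. The documents give no correlation rho between baseline and end-of-treatment lipids, so I take 0.5, 0.7 and 0.8. The formulas assume equal SD sigma at both visits and complete data.

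**Step 1: precision.** Variance of the arm contrast:

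- change score: (2/n) × 2(1 − rho) × sigma²
- ANCOVA: (2/n) × (1 − rho²) × sigma²
- ratio, ANCOVA to change score: (1 − rho²) / [2(1 − rho)] = (1 + rho)/2

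At 19 vs 19 the t-test detects 0.934 SD with 80% power. Multiply this by sqrt(2(1 − rho)) for the change score or sqrt(1 − rho²) for ANCOVA:

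| rho | variance ratio | detectable, change score | detectable, ANCOVA |
|---|---|---|---|
| 0.5 | 0.75 | 0.934 × 1.000 = 0.93 SD | 0.934 × 0.866 = 0.81 SD |
| 0.7 | 0.85 | 0.934 × 0.775 = 0.72 SD | 0.934 × 0.714 = 0.67 SD |
| 0.8 | 0.90 | 0.934 × 0.632 = 0.59 SD | 0.934 × 0.600 = 0.56 SD |

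In one simulated data set (19 per arm, rho 0.7), a random-intercept model with free baseline means gave the change-score result: 0.522, SE 0.288. ANCOVA gave 0.483, SE 0.251. A mixed model with baseline means constrained equal gave 0.489, SE 0.262. Over 4,000 runs at each rho, the equal-baseline estimator had an SE of 0.994 to 0.995 of ANCOVA's.

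**Step 2: power with the SAP's position and starter terms in both models.** Simulation with 38 players, a true difference of 0.6 SD and an assumed position mix:

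| rho | change score | ANCOVA |
|---|---|---|
| 0.5 | about 42% | about 50% |
| 0.7 | about 59% | about 65% |
| 0.8 | about 78% | about 81% |

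**Step 3: the covariate list read literally.** With both visits as responses and only a treatment main effect, the expected coefficient for a true end-of-treatment difference delta is (0 + delta)/2 = delta/2. For delta = 0.6 SD that is 0.30 SD. At rho 0.5 without strata, its SE is sqrt((2/19) × 0.75) = 0.281, so 0.30/0.281 = 1.07 and power is about 19% (1.07 − 1.96 = −0.89 on the normal scale). The t-test figures without strata are 44% for the change score and 55% for ANCOVA. In the data set of Step 1 the main effect was 0.165 against 0.522 from the interaction. It fell below half of 0.522 (0.261) because of a chance baseline imbalance.

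**Step 4: individual change.** Two visits give three moments (two variances and one covariance). A random intercept, random slope, their covariance and a residual need four parameters. The sets (0.7, 0, 0, 0.3) and (0.8, 0.2, −0.1, 0.2), in the order intercept variance, slope variance, covariance, residual, both imply [[1, 0.7], [0.7, 1]]. Slope variances of 0 and 0.2 therefore cannot be told apart. A random intercept alone is identified.

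**The case against.** The strongest reply is that the SAP commits only to a framework. It names no random slope and no free-baseline contrast, so criticising either is criticising a model that is not on the page. A reader might infer that a mixed model with two visits cannot address individual change at all, or is always less precise than ANCOVA. The documents support neither inference. A random-intercept model is estimable, each player's observed change can be computed, and a mixed model with equal baseline means matches ANCOVA's precision. Nor can observed individual change be called mere noise, since no document gives the reliability of the lipid measurements. All of this stands. What remains is that the text does not select one of the sound versions, and the terms it does list point towards the weaker ones.

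A second reply is that ANCOVA with starter status and eight position groups spends up to 11 parameters on 38 players (intercept, baseline, treatment, one for starter status, seven for position), which could erase the gain. If that model is set against a change score with no strata, the gain does vanish at rho 0.8 (80% vs 80%). But the SAP already includes position and starter status, so they belong in both models, and baseline then costs one further parameter. On that basis a gain remains, though at rho 0.8 it is only about three percentage points.

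A third reply is fair: moving lipids to ANCOVA must not silently drop age, genotypes and the treatment-by-starter interaction, and it does not repair the missing treatment-by-visit term for the four-visit markers.

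**Conclusion.** The concern holds as one of under-specification. A primary outcome with two visits has no model description that fixes how baseline is handled or where the treatment effect is read. Depending on the unstated choice, the cost is a change-score contrast (ANCOVA would have 0.75 to 0.90 of its variance) or, on the literal covariate list with baseline among the responses, an estimate of about half the true effect. The dilution is the more serious of the two. The precision loss is modest: about 8, 6 and 3 percentage points of power at rho 0.5, 0.7 and 0.8 for a 0.6 SD difference with 38 players. These sizes rest on an assumed rho, 19 per arm, equal SDs, complete data and an assumed position mix. On individual change the point is limited: modelled player-specific slopes cannot be separated from measurement error with two visits, but observed changes can be described.

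**What to change.** In the SAP's section on continuous outcome measures, give the lipid panel its own sentence. For TG (log scale), HDL-C, LDL-C and total cholesterol, make the primary arm contrast an ANCOVA of the end-of-treatment value on baseline value, treatment, starter status and position group. An equivalent is a random-intercept mixed model with both visits as responses, baseline means constrained equal and a treatment-by-visit term. Keep age, genotypes and the treatment-by-starter interaction as planned, or state that they are secondary. State that player-specific modelled slopes will not be reported for two-visit outcomes, and that observed individual change is descriptive. While editing, name the treatment-by-visit term for the four-visit markers too.

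The cost is a few SAP sentences and no new data. Plain ANCOVA drops players without an end-of-treatment panel; the constrained mixed model keeps players with one missing panel. Because the protocol records the study as completed, the change should be a dated clarification, disclosed as such, stating whether it preceded unblinded analysis of the lipid data.
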